8.1.1 Survey Assessments

We will use surveys to assess the remaining secondary outcomes as well as other social and community resources and barriers related to health. The secondary outcomes include oral health knowledge, oral health behavior, attitudes towards oral health care and maternal/child health knowledge. These are described in Section 3.2. Other domains include social determinants of health (e.g., insurance, transportation; physical living conditions; social support), and trust and satisfaction with the CHR. Specific survey items and scoring are in the MOP.

9 ASSESSMENT OF SAFETY

9.1 Specification of Safety Parameters

Safety parameters will include all serious adverse events (SAEs) experienced by participants in this study. Unanticipated problems (UPs) occurring in the research will also be reported as per IRB requirements.

9.1.1 *Unanticipated Problems*

The Office for Human Research Protections (OHRP) considers unanticipated problems involving risks to subjects or others to include, in general, any incident, experience, or outcome that meets **all** of the following criteria:

- unexpected in terms of nature, severity, or frequency given (a) the research procedures that are described in the protocol-related documents, such as the IRB-approved research protocol and informed consent document; and (b) the characteristics of the subject population being studied;
- related or possibly related to participation in the research (“possibly related” means there is a reasonable possibility that the incident, experience, or outcome may have been caused by the procedures involved in the research); and
- suggests that the research places subjects or others at a greater risk of harm (including physical, psychological, economic, or social harm) than was previously known or recognized.

9.1.2 *Adverse Events*

An adverse event is any untoward or unfavorable medical occurrence in a human subject, including any abnormal sign (for example, abnormal physical exam or laboratory finding), symptom, or disease, temporally associated with the subject's participation in the research, whether or not considered related to the subject's participation in the research.

9.1.3 *Serious Adverse Events*

A serious adverse event (SAE) is one that meets one or more of the following criteria:

- Results in death
- Is life-threatening (places the subject at immediate risk of death from the event as it occurred)
- Results in inpatient hospitalization or prolongation of existing hospitalization
- Results in a persistent or significant disability or incapacity
- Results in a congenital anomaly or birth defect

- An important medical event that may not result in death, be life threatening, or require hospitalization may be considered an SAE when, based upon appropriate medical judgment, the event may jeopardize the subject and may require medical or surgical intervention to prevent one of the outcomes listed in this definition.

9.2 Time Period and Frequency for Event Assessment and Follow-Up

The PI will record all events with start dates occurring any time after informed consent is obtained until 7 (for non-serious AEs) or 30 days (for SAEs) after the last day of study participation for those completing the full study period and who agree to be recontacted. At each study visit, the CHR will inquire about the occurrence of AE/SAEs since the last visit. Events will be followed for outcome information until resolution or stabilization.

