5.5 Participant Withdrawal or Discontinuation from Study Procedures/Intervention

5.5.1 Reasons for Participant Withdrawal or Discontinuation from Study Procedures/Intervention

Participants are free to withdraw from participation in the study at any time upon request. If a family has a child with an identifiable high needs condition at birth they may choose to withdraw as they may need to focus time on those needs.

Participants may choose to discontinue the intervention or study procedure but continue to be followed.

Mother-child dyads may be withdrawn from the study if the child is born with congenital oral anomalies expected to adversely affect the development of primary teeth, ectodermal dysplasia, or diseases other than ECC that affect the dentition or oral mucosa upon examination. This includes children with ulcerative gingivitis, stomatitis or other conditions resulting in chronically disrupted or irritated oral mucosa as reported by parent/caregiver or documented by a dental professional.

Mother-child dyads may be withdrawn from the study if the study child is allergic to any of the components of the FV as reported by parent/caregiver

Participants will also be withdrawn if informed consent is withdrawn by the parent/guardian or if they move permanently from the area.

An investigator may discontinue an individual's participation in an intervention or withdraw an individual from the study if:

- Any clinical adverse event (AE), laboratory abnormality, or other medical condition or situation occurs such that continued participation in the study would not be in the best interest of the participant.
- The participant meets an exclusion criterion (either newly developed or not previously recognized) that precludes further study participation.

5.5.2 Handling of Participant Withdrawals from Study or Participant Discontinuation of Study Intervention

If the mother/caregiver wants to drop out of the study early, we will ask if they wish to stop the intervention or drop out of the study entirely. If they want to stop the intervention, we will ask if they are willing to continue to be followed without the intervention and permit additional caries assessment(s). The purpose of this is to collect sufficient data to be able to conduct a more robust intent-to-treat analysis.

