If a mother/caregiver drops out of the study early and refuses additional follow-up, an early termination visit will be requested. If this request is accepted, a dmfs measure for the child will be obtained along with a questionnaire to the mother/caregiver about dental knowledge, attitudes, and behavior; psychological influences; other health and risk factors; other dental interventions received; and the reasons for early termination.

If the mother/caregiver wants to withdraw from the study entirely we will include their data to that point in the analyses. If the mother/caregiver wants to completely withdraw consent then that record will be excluded from all analyses, including the intention-to-treat analysis. All withdrawals and discontinuations will be recorded using the Case Report Form.

If a person other than the mother becomes the child's primary caregiver we will invite that person to participate so that the child may continue in the study. We would complete informed consent to enroll the new caregiver. Although we expect this to be rare, the advantage of maintaining the child's participation would outweigh the disadvantage of a caregiver that does not receive the full set of intervention sessions. Caregivers meeting inclusion criteria 1, 2, 3 and 6 in Section 5.1 would be eligible to enroll. Caregiver changes will be tracked and any study visits occurring prior to the change will be noted as missed interventions.

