7.5 Withdrawal Visit

If a mother/caregiver/child drops out of the study early and refuses additional follow-up, an early termination visit will be requested. If this request is accepted, a dmfs measure for the child will be obtained along with a questionnaire to the mother/caregiver about sociodemographic factors; dental knowledge, attitudes, and behavior; psychological influences; other health and risk factors; other dental interventions received; and the reasons for early termination. If the early termination visit is refused, we will ask if they are willing to continue to be followed without the intervention. If the participant wishes to fully withdraw we will withdraw them and their child from the study.

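### Section 9.2 gives the 7-day and 30-day post-participation safety windows to completers only, so events that begin after a dyad leaves the study entirely have no collection rule

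*Combined protocol and SAP*

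**What the plan says.** Section 9.2 sets a common start for safety recording: "The PI will record all events with start dates occurring any time after informed consent is obtained". The same sentence sets the end at 7 days for non-serious events and 30 days for serious ones, counted as follows: "after the last day of study participation for those completing the full study period and who agree to be recontacted". The section adds a routine inquiry, "At each study visit, the CHR will inquire about the occurrence of AE/SAEs since the last visit", and says that events are followed until they resolve or stabilise. Section 9.4.2 repeats that follow-up rule for all SAEs.

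Several routes out of the study relate to safety. Section 5.5.1 lets the investigator discontinue or withdraw someone on a condition that turns on the participant's best interest and opens: "Any clinical adverse event (AE), laboratory abnormality, or other medical condition or situation occurs such that continued participation in the study would not be in". It also lets a dyad be withdrawn if the child is allergic to a varnish component. Section 2.3.1 says that children with known sensitivity to varnish ingredients will be withdrawn.

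For a family that leaves and refuses further follow-up, Sections 5.5.2 and 7.5 say that "an early termination visit will be requested". If the family accepts, the visit collects dmfs and a questionnaire whose listed topics end with "other dental interventions received; and the reasons for early termination". Neither section mentions a safety contact after that visit.

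**The concern.** The only rule for collecting events after participation ends depends on completing the study, and completion can itself depend on harm. A dyad removed for an adverse event or a varnish allergy is a non-completer by definition and so falls outside the window.

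The visit spacing sharpens this. Postnatal visits are about six months apart, so an event that begins after a family goes home is normally picked up at the next visit. A family that leaves has no next visit and, under 9.2, no window in its place.

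At stake is the completeness of SAE capture in the participants where a late reaction would matter most. Section 9.1 defines the safety parameters as all SAEs that participants experience, and the safety review in 9.5 and DSMB oversight in Section 10 rely on those reports. Planned varnish exposure also differs by arm (6, 12, 18 and 24 months against 12 and 24 months, Section 4), so missed events need not fall evenly.

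**Working it through.** **Coverage, by type of event and participant**

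| Situation | Rule in the protocol |
|---|---|
| Event starts between consent and exit, any participant | Recordable (9.2) |
| Event already recorded at exit | Followed until resolved or stable (9.2; 9.4.2 for SAEs) |
| Dyad stops the intervention but stays in follow-up | Can complete the study period, so keeps the window (5.5.1, 5.5.2) |
| New event within 7 or 30 days after the last day, completer who accepts recontact | Recorded (9.2) |
| New event after full exit, early leaver | No rule found |

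Only the last row is open.

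**How many dyads.** Inputs from Section 12.2: 350 enrolled, 19% attrition. The plan's retained number reproduces: 350 × (1 − 0.19) = 283.5. The complement is 350 × 0.19 = 66.5, about 66 dyads or 33 per arm. This treats all attrition as early exit.

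**Share of post-participation events.** Let r be the event rate in leavers relative to completers (an assumption; the documents give no figure). If everyone had a window, the leavers' share of events in it would be 0.19r / (0.19r + 0.81):

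- r = 1: 0.19 / 1.00 = 19%
- r = 2: 0.38 / 1.19 = 32%
- r = 4: 0.76 / 1.57 = 48%

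These shares describe the tail after participation only.

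**Share of all SAEs.** Participation lasts T = 29 to 41 months (Protocol Summary). Further assumptions: constant event rates, leavers exit halfway on average, 30 days counted as one month, and all completers accept recontact. The share of all SAEs that falls in the leavers' missing 30-day tail is

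0.19r / [0.81(T + 1) + 0.19r(T/2 + 1)]

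- r = 1, T = 29: 0.19 / (24.30 + 2.945) = 0.70%
- r = 1, T = 41: 0.19 / (34.02 + 4.085) = 0.50%
- r = 4, T = 29: 0.76 / (24.30 + 11.78) = 2.1%
- r = 4, T = 41: 0.76 / (34.02 + 16.34) = 1.5%

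The missing tail is a large part of the post-participation window but a small part of the whole safety record.

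**The case against.** The strongest reply is that early leavers already have most of the protection that matters. Recording from consent to exit applies to everyone, and the event that prompted a removal would be on record and followed. This stands. A reader might infer from 9.2 that early leavers have no safety coverage at all, or that a reaction already recorded would be lost if it worsened after exit. The documents do not support either reading.

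A second reply concerns the early-termination visit. Its listed contents omit an adverse event check, and a reader might infer that none is made. That is not established. The 9.2 inquiry applies at each study visit, which can cover the Withdrawal Visit in Section 7.5. The visit lists are not exhaustive, since Visit 7 (Section 7.4) also lacks the adverse event line. The Premature Discontinuation column of Appendix A is unreadable in the supplied text. What remains is that the visit is optional and, even with an inquiry, is a check at exit and not a window after it.

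A third reply is that the numbers are small and partly beyond repair. Much attrition will be families who cannot be contacted (Section 5.3 defines loss to follow-up by failure to schedule the final dental assessment), and anyone who leaves before the child's first varnish application has no varnish exposure. Section 2.3.1 cites a review of three trials with no varnish-related adverse events. This limits the size of the problem. It does not explain why a reachable and willing early leaver should be outside the rule.

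**Conclusion.** The point holds in a narrow form. Section 9.2 restricts the post-participation windows to completers who accept recontact, and nothing else in the protocol covers new-onset events after full exit, including for dyads removed for an adverse event or varnish allergy.

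At most about 66 of 350 dyads are affected, assuming 19% attrition that is all early exit. The number the fix could help is lower, because some families cannot be reached.

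A reader might infer that overall AE and SAE rates will be materially biased downward. The documents do not show that. Under the assumptions above the missing tail holds about 0.5% to 2.1% of SAEs, and rates calculated on observed person-time need not be biased downward by a shorter window. The constant-rate assumption could understate risk just after an exit caused by harm, and the documents give no figure for that. The case for change rests on capturing individual late events in a group where they are most relevant, at low cost.

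**What to change.** In 9.2, remove the completer condition so that the existing 7-day and 30-day windows run from the last day of participation for every participant who has not withdrawn consent to contact. Say which date counts as the last day for a dyad that leaves early.

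In 5.5.2 and 7.5, state that the 9.2 AE/SAE inquiry is made at the early-termination visit, and check that the Premature Discontinuation column of Appendix A agrees.

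The cost is edits to three sections, a check of one table, and one extra contact attempt per willing early leaver. A single contact after day 30 can ask about both windows. Some families will not be reached, and those who withdraw consent to contact stay outside the window.

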9.3 Characteristics of an Adverse Event

Each event will be recorded on an appropriate case report form that includes assessment of the characteristics defined below. These characteristics, along with the frequency of an event's occurrence, will be considered in determining if the event is a UP.

9.3.1 Relationship to Study Intervention

To assess relationship of an event to study intervention the following guidelines are used:

1. Related (Possible, Probable, Definite)
 - a. The event is known to occur with the study intervention, and/or
 - b. There is a temporal relationship between the intervention and event onset and/or
 - c. The event abates when the intervention is discontinued, and/or
 - d. The event reappears upon a re-challenge with the intervention.
2. Not Related (Unlikely, Not Related)
 - a. There is no temporal relationship between the intervention and event onset, and/or
 - b. An alternate etiology has been established.

9.3.2 Expectedness

The PIs will be responsible for determining whether an AE is expected or unexpected. An adverse event will be considered unexpected if the nature, severity, or frequency of the event is not consistent with the risk information previously described for the intervention.

9.3.3 Severity of Event

The following scale will be used to grade adverse events:

1. Mild: no intervention required; no impact on activities of daily living (ADL)
2. Moderate: minimal, local, or non-invasive intervention indicated; moderate impact on ADL
3. Severe: significant symptoms requiring invasive intervention; subject seeks medical attention, needs major assistance with ADL

9.4 Reporting Procedures

9.4.1 Unanticipated Problem Reporting

Incidents or events that meet the OHRP criteria for unanticipated problems require the creation and completion of an unanticipated problem report form. OHRP recommends that investigators include the following information when reporting an adverse event, or any other incident, experience, or outcome as an unanticipated problem to the IRB:

- appropriate identifying information for the research protocol, such as the title, investigator's name, and the IRB project number;
- a detailed description of the adverse event, incident, experience, or outcome;
- an explanation of the basis for determining that the adverse event, incident, experience, or outcome represents an unanticipated problem;
- a description of any changes to the protocol or other corrective actions that have been taken or are proposed in response to the unanticipated problem.

To satisfy the requirement for prompt reporting, unanticipated problems will be reported using the following timeline:

- Unanticipated problems that are serious adverse events will be reported to the IRB within **10 business days** (as per NAU guidelines; https://nau.edu/wp-content/uploads/sites/74/2018/05/Reporting-Local-Information_v2019.8.pdf) of the investigator becoming aware of the event. Any other unanticipated problem will be reported to the IRB within **10 business days** of the investigator becoming aware of the problem
- All unanticipated problems should be reported to appropriate institutional officials (as required by an institution's written reporting procedures), the supporting agency head (or designee), and OHRP within one month of the IRB's receipt of the report of the problem from the investigator.

All unanticipated problems will be reported to NIDCR Medical Monitor concurrently with reporting to the IRB. These reports will be made to NIDCR's centralized reporting system via Rho Product Safety:

- Product Safety Fax Line (US): [name]
- Product Safety Fax Line (International): [contact]
- Product Safety Email: [contact]

General questions about UP reporting can be directed to the Rho Product Safety Help Line (available 8:00AM – 5:00PM Eastern Time):

- US: [name]
- International: [contact]

9.4.2 Serious Adverse Event Reporting

Any AE meeting the specified Serious Adverse Event criteria will be submitted on an SAE form to NIDCR's centralized safety system via Rho Product Safety. This report may be sent by fax or email. Once submitted, Rho Product Safety will send a confirmation email to the investigator within 1 business day. The investigator should contact Rho Product Safety if this confirmation is not received. This process applies to both initial and follow-up SAE reports.

SAE Reporting Contact Information:

- Product Safety Fax Line (US): [name]
- Product Safety Fax Line (International): [contact]
- Product Safety Email: [contact]

General questions about SAE reporting can be directed to the Rho Product Safety Help Line (available 8:00AM – 5:00PM Eastern Time):

- US: [name]
- International: [contact]

The study's clinically responsible individual will complete a Serious Adverse Event Form and submit via fax or email within the following timelines:

- All deaths and immediately life-threatening events, whether related or unrelated, will be recorded on the Serious Adverse Event Form and submitted to Product Safety within **1 day** (as per NAU IRB requirements) of site awareness.
- Serious adverse events other than death and immediately life-threatening events, regardless of relationship, will be reported by fax within 10 days of site awareness.

All SAEs will be followed until resolution or stabilization.

9.4.3 Reporting of Safety Events to FDA

Not applicable

9.4.4 *Events of Special Interest*

Not applicable.

9.4.5 *Reporting of Pregnancy*

Not applicable.

9.5 Halting Rules

The frequency of UPs or SAEs in this study is expected to be very small. If the number of SAEs is unexpectedly large, or of a particular type, NIDCR and the DSMB may consider temporarily suspending enrollment to the study and the study intervention until a safety review is convened. The objective of the safety review would be to make a decision on whether the study should continue per protocol, proceed with caution, be further investigated, be discontinued, or be modified and then continued.

10 STUDY OVERSIGHT

In addition to the PI's responsibility for oversight, study oversight will be under the direction of a Data and Safety Monitoring Board (DSMB) appointed by the NIDCR. The DSMB will operate under the rules of an NIDCR-approved charter that will be approved at the organizational meeting of the DSMB. The conduct of the DSMB and rules regarding how often the Board will meet will be defined by the DSMB charter for the study. At this time, most data elements that the DSMB needs to assess will be clearly defined. It is anticipated that the DSMB will meet at least once per year via teleconference to assess safety and efficacy data, study progress, and data integrity for the study. If safety concerns arise, more frequent meetings may be held. The DSMB will operate under the rules of an NIDCR-approved charter that will be approved at the organizational meeting of the DSMB. At this time, most data elements that the DSMB needs to assess will be clearly defined. The DSMB will provide recommendations to the NIDCR.

11 CLINICAL SITE MONITORING

Clinical site monitoring is conducted to ensure that the rights of human subjects are protected, that the study is implemented in accordance with the protocol and/or other operating procedures, and that the quality and integrity of study data and data collection methods are maintained. Monitoring for this study will be performed by the NIDCR's Clinical Research Operations and Management Support (CROMS) contractor. The monitor will evaluate study processes and documentation based on the International Council for Harmonisation (ICH), E6: Good Clinical Practice guidelines (GCP).

Details of clinical site monitoring will be documented in a Clinical Monitoring Plan (CMP). The CMP will specify the frequency of monitoring, monitoring procedures, the level of clinical site monitoring activities (e.g., the percentage of participant data to be reviewed), and the distribution of monitoring reports. Some monitoring activities may be performed remotely, while others will take place at the study site(s). Staff from CROMS will conduct monitoring activities and provide reports of the findings and associated action items in accordance with the details described in the CMP. Documentation of monitoring activities and findings will be provided to the site study team, the study PIs, NIDCR-OCTOM, and NIDCR Program staff. The NIDCR reserves the right to conduct independent clinical site monitoring as necessary.

